The aim of the present project is to demonstrate the impact of the modulation of executive functions, particularly subserved by DLPFC, on language production in healthy bilingual. We propose that such impact will be particularly present in non-native languages (L2).

The project will tackle the question of the role of prefrontal system and executive functioning (namely updating/working memory system, subserved by the left DLPFC) in language performance in the L1 and in L2. The core question will be whether stimulation of DLPFC will influence lexical access and language production.

The experimental task will test the impact of prefrontal stimulation by rTMS (excitatory, inhibitory, sham) applied to the DLPFC of healthy adult bilingual subjects during two tasks relying on lexical strategies: a picture naming task in L1 and L2 and a word translation task. The EEG correlates of the two tasks performed in the first and second language following rTMS will be analyzed. The EEG study will allow us to investigate precisely the spatiotemporal brain dynamics underlying the behavioral modifications induced by the modulation of left frontal areas.

The hypothesis is that:

1. Excitatory rTMS applied to the left DLPFC will increase performance and/or decrease response time in naming, particularly in L2 naming and in the translation task versus sham and inhibitory rTMS.
2. Excitatory rTMS is expected to modify the cortical activity related to the language tasks. During naming, EEG analyses will show a main effect of stimulation and an interaction between the factors Language (L1 or L2) and Stimulation (excitatory rTMS versus sham and inhibitory rTMS versus sham) at the topographic level, showing an effect of prefrontal areas larger in L2 than L1. The latency of the ERP modulation by rTMS in L2 will allow us to target the dynamics and the language planning processes) underlying improved naming performance.

Methods:

The experimental task will include 80 healthy L1-L2 unbalanced control subjects. We will analyze the influence of the DLPFC activation and inhibition on naming and complex language production task (i.e. translation ability) using rTMS as well as their EEG correlates in L1 and in their best second language (L2). The prediction is that left prefrontal stimulation will increase language performances particularly in L2. EEG analyses will unravel the spatio-temporal dynamics of executive processes involved in the two tasks.

EEG

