To assess language immersion, participants will be asked for the age of acquisition, how long they lived in a region where predominantly German and English language was spoken, the language spoken with family members, when they were child, in their current daily life, and if the language was acquired in or out of school. With regards to the self-evaluation part, participants will indicate in an analogue scale from 1 to 100% how they estimate their reading, speaking, comprehension and writing skills. As a third level of assessment, a sub-test from the computer-based DIALANG language diagnosis system (Zhang and Thompson, 2004 [14]) will be used to evaluate reading performance (see Buetler et al 2014 for a similar procedure [15]).

Procedure

Participants will be randomized to take part in either an inhibitory or excitatory rTMS session. In all sessions, the same evaluations/tasks will be used. Each session starts with sham rTMS-controlled baseline tasks.

At the beginning of the session, the individual motor threshold for the subject's relaxed small hand muscles will be determined by stimulating the right motor cortex with single pulses (e.g. Nyffeler et al., 2008 [16]). This will last about 5-10 minutes. For the rTMS session, we will be using a "theta-burst" rTMS protocol (Nyffeler et al., 2008 [16]; Huang et al., 2005 [17]), in which one of the co-applicants has extensive experience. This stimulation takes 30 seconds to 5 minutes and the resulting effects have been shown to last about 30 minutes. Each rTMS session will be conducted following suggested international rTMS guidelines (Wassermann et al., 1998 [18]).

After applying rTMS, two language tasks will be performed by the participants while an EEG will be recorded. The two language contexts (German and English) will be presented within each of the two sessions in a randomized order. EEG electrodes will be applied before the stimulation. Participants will be seated in an electrically shielded and sound attenuated booth in front of a LCD screen. Stimulus delivery and response recording are controlled using E-Prime 2.0 (Psychology Tools, Inc., Pittsburgh, PA). The stimuli will be presented in the center of the screen. Both behavioral and EEG data will be recorded.

Stimuli and tasks

This study will be conducted in parallel to the previously accepted study A. For this second addendum, there will be no translation task and a different non-verbal task.

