Verbal and nonverbal switching task during EEG recording

Right after applying rTMS (inhibitory/excitatory/sham), participants will perform a language switching task during the EEG recording. The switching task will be based on a corpus of 520 pictures, the corresponding words being matched in English and German on pertinent psycholinguistic factors (Bates et al 2003 [19]). The stimuli consist of black and white line drawings (of 8.5 x 8.5cm each) representing manufactured or living objects. Right before the picture appears on the screen, a cue will be given to the participants in order to indicate the language in which they have to name the object. The subject will then have 3500 - 4500 ms to name the object.

Moreover, participants will also perform a non-verbal switching task during the EEG recording. In this task, participants have to switch frequently between high/low and odd/even classifications of a digit, based on the method of Monsell, Sumner and Waters (2003) Before each digit appears, a cue will be given to indicate to which classification criteria participants have to respond.

Translation task to L1 and L2 during EEG recording

Moreover, participants will perform a task consisting of translating 100 words (5 letters length) from L1 to their second language (L2) or vice versa (8 minutes). Both senses of translation will be mixed randomly to increase working memory load. Translation corpus consists of 50 words in each language, matched across L1 and L2 on frequency, length in syllables and phonemes. Words will be presented on the screen and the subject will be asked to translate each word in the other language. The words will be presented 1500 ms on the screen after a fixation cross of 300ms. The subject will have a maximum 2500ms to do the translation.

Verbal and non-verbal fluency tasks, without EEG recording

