With the specific stimulation parameters used in our protocol, 30 minutes after applying rTMS (inhibitory/excitatory), it can be assumed that the after-effect of the stimulation will have disappeared. Participants will then perform a verbal fluency task (the subject will be asked to name as many words as he/she can which starts with a certain letter during 1 minute). Furthermore, a non-verbal fluency task (5 points test, i.e. a sheet of paper with 40 squares of fixed symmetrically arranged points (5 points) will be presented to the participant. The participant will be asked to produce as many different figures as possible with connecting the dots with at least one line connecting two dots during 2 minutes). Finally, participants will perform a 1-minute verbal fluency task in L2.

Behavioral and EEG analyses

Behavioral analysis

A first behavioral analysis will compare naming and translation performances, as well as speech onset latencies in both languages.

For statistical analyses we will compute two 2 way-ANOVAs for repeated measures with the within-subject factors *Language* (L1 vs L2) and *Stimulation* (inhibitory vs sham or excitatory vs sham). Moreover, we will compute two mixed-model ANOVAs with *Language* (L1 vs L2) as within-subject factor and *Hemisphere* (left vs. right) or *Stimulation* (inhibitory vs excitatory) as between-subject factors.

Event Related Potentials analyses

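### Study A does not say how pictures are assigned to the Language × Stimulation cells, and its within-subject ANOVAs have no picture term, so a fixed list per cell could pass for an interaction

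*Combined protocol and SAP*

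**What the plan says.** Under Study A, Behavioral analysis, the outcomes are introduced thus: "A first behavioral analysis will compare naming and translation performances, as well as speech onset latencies in both languages". The tests follow: "we will compute two 2 way-ANOVAs for repeated measures with the within-subject factors" Language (L1, L2) and Stimulation (inhibitory against sham in one ANOVA, excitatory against sham in the other). Then: "Moreover, we will compute two mixed-model ANOVAs with" Language within subjects and either Hemisphere or type of stimulation between subjects. No picture factor, by-item analysis or trial-level model is named. Averaging to one value per participant and cell is implied by these models but not stated.

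On the pictures, the section on the verbal and nonverbal switching task says: "The switching task will be based on a corpus of 520 pictures", with "the corresponding words being matched in English and German on pertinent psycholinguistic factors". A cue before each picture sets the naming language. The documents do not give the number of pictures each participant names. Nor do they say whether pictures repeat across languages or between sham and active runs, or whether lists are fixed, rotated or randomised.

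On the design: "The experimental task will include 80 healthy L1-L2 unbalanced control subjects" and "Participants will be randomized to take part in either an inhibitory or excitatory rTMS session". The Procedure places a sham-controlled baseline at the start of each session, so active against sham is a within-person comparison. The Stimuli and tasks section drops the translation task from this addendum, so picture naming carries the behavioural language question.

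**The concern.** Naming data are trials crossed over participants and pictures, and pictures differ in how quickly and accurately they are named. The interaction contrast for each participant is

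d = (L2 active − L2 sham) − (L1 active − L1 sham).

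If the four cells use four different sets of pictures, d contains the difference in difficulty between those sets. Matching the English word to the German word for the same picture does not make the sham set as easy as the active set.

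What follows depends on the assignment. With the same list in a given cell for everyone, the list difference shifts every d by the same amount. The by-participant error term cannot detect it, and adding participants makes the problem worse. With a fresh random split for each participant, the list difference averages out and only adds variance. In the first case, a significant result could not be told apart from an easier list.

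**Working it through.** Study A states no alpha, SD, effect size, power or sample-size calculation, so there is no figure of the plan's own to reproduce.

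**Inputs from the documents:** 80 participants, two rTMS arms, 520 pictures, a 2 × 2 within-subject test.

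**Assumptions:** 1:1 allocation, so n = 40 per within-subject ANOVA (20 and 80 also tried); each picture named once, so m = 520/4 = 130 per cell (65 also tried); two-sided alpha 0.05; trial SD s_e = 200 ms; picture SD left after matching s_i = 20, 50 or 100 ms; SD between participants in the true interaction τ = 0 or 40 ms.

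**Formulas.** The one-sample t-test on d is equivalent to the 2 × 2 interaction F-test.

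- Variance of d without pictures: V = τ² + 4·s_e²/m
- Picture variance in d, four different lists: B = 4·s_i²/m
- Fixed list per cell: type I error = 2·[1 − Φ(1.96/√(1 + n·B/V))]
- Random lists per participant: error variance V + B in place of V

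**Worked example, s_i = 50, τ = 40, n = 40, m = 130.** V = 1600 + 4 × 40,000/130 = 2830.8. B = 4 × 2500/130 = 76.9. n·B/V = 1.087. Then 1.96/√2.087 = 1.357, so type I error is 17.5%. With random lists, V + B exceeds V by 76.9/2830.8 = 2.7%.

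**Results, n = 40, m = 130:**

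| Picture SD | Fixed lists: type I error, τ = 40 / τ = 0 | Random lists: extra error variance, τ = 40 / τ = 0 |
|---|---|---|
| 20 ms | 7.0% / 9.8% | 0.4% / 1.0% |
| 50 ms | 17.5% / 29.5% | 2.7% / 6.2% |
| 100 ms | 39.7% / 55.5% | 10.9% / 25.0% |

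Simulation (4000 runs per setting) agrees: 7.6–55.1% for fixed lists and 4.8–6.0% for random lists. With fixed lists and m = 130, the closed-form range is 6–42% at n = 20 and 9–67% at n = 80. With m = 65 and n = 40 it is 8–56%.

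At a picture SD of 75 ms, B = 4 × 5625/130 = 173.1. The extra variance with random lists is 173.1/2830.8 = 6.1% at τ = 40. It is 173.1/1230.8 = 14.1% at τ = 0, where participants do not differ at all in the true interaction.

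**Power with random lists**, at an effect set for 80% by the normal formula: 76% against 77–79% without picture noise at s_i = 50, and 69–74% against about 78% at s_i = 100.

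**Other assignments:**

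- Latin-square rotation with the planned ANOVA: simulated type I error 2.9–5.2%, valid to conservative.
- Same pictures in all four cells: intercepts cancel, about 5%.
- Same pictures in sham and active within each language: intercepts cancel in d, but the Language main effect compares different lists.
- Same pictures in both languages within each stimulation condition: intercepts cancel in d, but the Stimulation main effect compares different lists.
- Mixed ANOVA of inhibitory against excitatory, same fixed lists in both arms: 4.6–5.3%, because the list effect is common to both arms.

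**The case against.** The strongest reply is that any bias comes from the picture assignment, not from the ANOVA, and the plan does not state that assignment. With rotation the planned ANOVA is valid. With fixed, non-overlapping lists a mixed model cannot separate list from condition either. That is right, and it is why rotation comes first below.

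A reader might infer that the plan uses a fixed list per cell, and so that its test is invalid. The documents do not say so. The Procedure's statement that tasks are the same in all sessions is compatible with reusing pictures, though it does not establish it. Full repetition looks impractical: 520 pictures in both languages is 1040 trials, at least 1040 × 3.5 s ≈ 61 minutes if the naming window runs its full length, against an after-effect of about 30 minutes. Repeating a smaller subset remains possible.

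A reader might also extend the point to all of Study A's ANOVAs. It does not reach the inhibitory-against-excitatory interaction when both arms share lists.

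Nor can the behavioural interaction simply be called the study's central test. The core question in the Aim is whether stimulation influences language production. The first hypothesis expects better naming, particularly in L2, and the interaction is named explicitly for the EEG data.

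Finally, the size rests on assumed SDs. A trial SD of 220 ms, a participant interaction SD of 50 ms and picture SDs of 75–200 ms would give 23–58% under fixed lists. The documents support neither that range nor any other, and lists deliberately balanced on item properties would differ less than random draws. No figure is given here for accuracy.

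**Conclusion.** The point holds as a gap in the plan with a conditional risk. The two active-against-sham ANOVAs have no picture term, and the stated matching does not balance pictures between sham and active runs. If each cell has its own fixed list, the interaction test runs at about 7–56% instead of 5% with 40 per arm, under the assumptions above. If lists are randomised per participant, validity is intact. The loss is then small: under about 7% extra error variance for picture SDs up to 75 ms when τ is 40 ms, reaching 25% only at a picture SD of 100 ms with τ = 0. If pictures recur across stimulation or across language, the interaction is free of picture intercepts. Picture-by-condition variation remains, and the Language or the Stimulation main effect, respectively, is still exposed. The documents do not show which case applies, so they do not support saying that the planned test is invalid.

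**What to change.** 1. **Main fix: assignment.** State how pictures are assigned. Split them into four disjoint lists and rotate these over the four Language × run cells across participants, in a Latin square balanced within each rTMS arm. This secures validity even with the ANOVAs as planned. If the sponsor already rotates or randomises pictures, saying so closes the validity point. If pictures are reused, the plan should say in which cells.

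2. **Cheap improvement: analysis.** Analyse naming at trial level with crossed random effects for participant and picture, with slopes where estimable, and keep the planned fixed effects and contrasts. This recovers the list variance that rotation leaves in the by-participant error term. It does not replace rotation.

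The cost is four list files in the presentation software, a revised analysis paragraph and somewhat more analysis work. The random slopes may have to be simplified if the model does not converge, so the order of simplification should be written down beforehand. No extra participants or visits are needed.

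### Study A's comparison of the randomised inhibitory and excitatory arms does not adjust for the sham-run score that every participant already provides, and so gives up precision that would cost almost nothing to keep

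*Combined protocol and SAP*

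**What the plan says.** Study A, Methods, gives the sample size: "The experimental task will include 80 healthy L1-L2 unbalanced control subjects". The Procedure section sets the design: "Participants will be randomized to take part in either an inhibitory or excitatory rTMS session". It adds "In all sessions, the same evaluations/tasks will be used" and "Each session starts with sham rTMS-controlled baseline tasks". Each participant therefore has a score on the outcome tasks after sham and before active stimulation.

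The Behavioral analysis section uses sham as one level of Stimulation in two repeated-measures ANOVAs ("inhibitory vs sham or excitatory vs sham"), each within one arm. Two mixed-model ANOVAs follow, with Language within subjects and, between subjects, either Hemisphere or Stimulation ("inhibitory vs excitatory) as between-subject factors"). Only the one with Stimulation compares the randomised arms. No covariate, change from sham or proficiency term is named for it there or elsewhere in the supplied text.

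The Language proficiency assessment section collects age of acquisition, language exposure, a DIALANG reading sub-test and self-ratings ("participants will indicate in an analogue scale from 1 to 100% how they estimate their reading, speaking, comprehension and writing skills"). It requires an intermediate level of English.

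**The concern.** The first hypothesis predicts that excitatory stimulation will do better than inhibitory stimulation as well as better than sham. The first of these is a comparison between randomised arms, and it is the Stimulation contrast that randomisation protects. The within-arm contrasts with sham are not protected in that way: sham always comes first, so practice, fatigue and order move with stimulation.

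As planned, the between-arm test of the Stimulation main effect, or of either language alone, leaves stable differences between people in naming performance in its error term. The sham run measures much of that difference. Because it precedes active stimulation, adjusting for it cannot remove a treatment effect. It also corrects chance differences between the arms. With 40 per arm, the standard error of the difference in any baseline mean is √(2/40) = 0.22 SD, so a gap above 0.3 SD arises in about 18% of randomisations.

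**Working it through.** The documents give 80 participants but no power calculation, so there is no figure of theirs to reproduce.

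**Inputs.** From the documents: 80 participants, two randomised arms, a sham run before active stimulation, the same tasks. Assumed, because not stated: 1:1 allocation (40 per arm), two-sided 5%, 80% power, and r, the correlation between sham-run and active-run scores, shown over a range.

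**Unadjusted.** For a two-sample t test with 40 per arm (78 df), the noncentral t distribution gives a detectable difference of 0.634 SD.

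**Adjusted, Stimulation main effect or one language.** Adjustment multiplies the residual variance by 1 − r², and hence the detectable difference by √(1 − r²). At r = 0.7, for example, 0.634 × √0.51 = 0.453. The last two columns also charge one degree of freedom and an allowance for chance covariate imbalance.

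| r | 1 − r² | Detectable SD, 40 per arm | Same, with costs | 20 per arm, with costs |
|---|---|---|---|---|
| 0 | 1.00 | 0.634 | 0.639 | 0.922 |
| 0.3 | 0.91 | 0.605 | 0.609 | 0.880 |
| 0.5 | 0.75 | 0.549 | 0.553 | 0.799 |
| 0.7 | 0.51 | 0.453 | 0.456 | 0.659 |
| 0.8 | 0.36 | 0.381 | 0.383 | 0.553 |

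The 20-per-arm column covers the case where Hemisphere also splits the sample; unadjusted, the detectable difference is then 0.909 SD.

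**Cost if the covariate is useless.** For a 0.5 SD effect with 40 per arm, power falls from 59.8% to 59.2%. Adjustment breaks even at r of about 0.1 to 0.15.

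**Interaction.** The Language by Stimulation interaction is tested on each person's L2-minus-L1 difference, so the relevant covariate is the same difference in the sham run. Let a be the sham-to-active correlation in the same language, b the correlation between languages within a run, and c the correlation across both run and language. With equal variances, the correlation of the two differences is (a − c)/(1 − b). Two illustrative sets:

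- a = 0.6, b = 0.6, c = 0.5: 0.1/0.4 = 0.25. Variance left is 1 − 0.0625 = 94%, and the detectable effect is 0.634 × √0.9375 = 0.614 SD of the difference.
- a = 0.8, b = 0.7, c = 0.6: 0.2/0.3 = 0.67. Variance left is 56%, and the detectable effect is 0.473 SD of the difference.

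For the main effect averaged over languages, the corresponding correlation is (a + c)/(1 + b): 1.1/1.6 = 0.69 and 1.4/1.7 = 0.82, leaving 53% and 32% of the variance.

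**Why the covariate must be centred.** With a common slope β and an uncentred same-language sham score, the Language coefficient becomes the active-run L1–L2 gap minus β times the sham-run gap. If both gaps equal 1 and β = 0.7, the model reports 0.3 as the Language effect. Centring the sham score within each language restores the gap and leaves the Stimulation and interaction estimates unchanged.

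**The case against.** The sham score is not discarded. The plan uses it in the two within-arm ANOVAs, which test the versus-sham part of the first hypothesis. That is correct, but neither of them compares the arms, so the omission from the between-arm test stands.

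The effect the plan stresses most is the interaction, explicitly for the ERPs and by its emphasis on L2 for behaviour. There, general naming speed has already cancelled in L2 minus L1, and at the low end of the illustration the gain is almost nil. This stands and limits the claim.

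Three stronger readings are tempting, and the documents do not support them:

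- *That the planned analysis is invalid.* It is not. Randomisation protects the unadjusted comparison; the loss is one of precision.
- *That adjustment would nearly double the effective sample.* At r = 0.7, 80/0.51 gives about 157, but no r appears in the documents; at r = 0.3 the figure is 80/0.91, about 88. The 40 per arm is also assumed, as no allocation ratio is stated.
- *That leaving out proficiency is a comparable loss.* Entry is restricted to an intermediate level, which narrows its range. For a 0.5 SD effect with 40 per arm and a sham covariate at r = 0.7, power is 86.7%. Adding a proficiency measure with partial correlation 0.1, 0.2 or 0.3 gives 86.6%, 87.6% or 89.2%.

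**Conclusion.** The point holds as a missed gain in precision. The one behavioural test of the randomised arms omits a valid pre-stimulation covariate that every participant supplies. For the Stimulation main effect or a single language, the detectable difference would fall by about 5% at r = 0.3 and by about 29% at r = 0.7 (1 − √0.51). For the interaction the illustrative fall is between about 3% and 25%. All of these rest on assumed correlations. The absolute values also assume 40 per arm, two-sided 5% and 80% power, and are worse throughout if Hemisphere divides the sample. The omission is certain from the text; the size of the gain is not. Since the worst case is about half a percentage point of power, adjusting is the better choice across any plausible range of r.

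**What to change.** Replace the between-arm mixed ANOVA with a prespecified ANCOVA or linear mixed model of the post-stimulation score. It should contain Stimulation, Language, their interaction, and the sham-run score in the same language, centred within language. For the interaction alone, the same aim is met by regressing the active-run L2-minus-L1 difference on arm and the sham-run L2-minus-L1 difference. Covariate adjustment is preferable to analysing change from sham: the change score has variance 2(1 − r), which at r = 0.5 equals the unadjusted variance, against 0.75 with the covariate.

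A proficiency covariate is optional. If one is wanted, name a single measure in advance and include its interaction with Language.

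Reconcile the Procedure section, which randomises each participant to one type of session but then refers to two sessions when describing the language contexts. Until that is settled, it is unclear which sham run is the covariate. State the allocation ratio, and whether Hemisphere divides the Study A sample.

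The cost is a few sentences of text and about one degree of freedom. No new data or procedures are needed, and fixing the covariate in advance prevents its being chosen after the results are seen.

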The analyses will be conducted with the same principles as in our prior works with reading and naming tasks. ERPs will be analyzed using a step-wise procedure that permits the time-wise, multifactorial statistical assessment of (1) the dynamic changes of scalp-recorded electric field configuration and their temporal segmentation into quasi-stable functional micro-states indexing modulations of the configuration of intracranial generators, (2) global electric field power indexing modulation of response strength of the intracranial generators, (3) intracranial distributed linear electrical source estimations (e.g. Brunet et al., 2011 [21]; Murray et al., 2008 [22]). These analyses will be conducted for each time frame of the whole ERP time-period; however, specific time windows are planned to be sensitive to our factors according to meta-analyses [19] and our previous results: lexical selection is thought to occur between 170 and 270 ms after picture presentation, so there will be a first time window until 200 ms, a second time window between 200 and 300 ms, and a later time window (300-450 ms) corresponding to lexical-phonological encoding in previous studies. The main effect will be L1 and L2 patterns in term of amplitude, duration and sequences. Then, a second main effect will be the left inhibitory/excitatory/sham effect in an early time window before the vocalization will start. We will expect an interaction between language and stimulation, due to the fact that left DLPFC excitatory rTMS will modulate L2 more than L1.

References

1. Green, D.W., et al., Language control and parallel recovery of language in individuals with aphasia. *Aphasiology*, 2010. 24(2): p. 188-209.
2. Abutalebi, J., et al., Bilingual aphasia and language control: a follow-up fMRI and intrinsic connectivity study. *Brain Lang*, 2009. 109(2-3): p. 141-56.
3. Machii K. et al. 2006. Safety of rTMS to non-motor cortical areas in healthy participants and patients. *Clinical Neurophysiology*, 117, 455-471.
4. Lefaucheur JP et al., 2014. Evidence-based guidelines on the therapeutic use of repetitive transcranial magnetic stimulation (rTMS). *Clinical Neurophysiology*, 125, 2150-2206.
5. Osaka N et al., 2007 Transcranial magnetic stimulation (TMS) applied to the left dorsolateral prefrontal cortex disrupts verbal working memory performance in humans. *Neuroscience Letters*, 418, 232-235.

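### Study A: ERP effects are all timed from picture presentation, so a change in naming speed could appear as changed activity at a language stage, and no planned analysis is set up to tell the two apart

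*Combined protocol and SAP*

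**What the plan says.** The section on Event Related Potentials analyses takes its clock from picture presentation: "lexical selection is thought to occur between 170 and 270 ms after picture presentation". From this it derives a single series of windows, "so there will be a first time window until 200 ms, a second time window between 200 and 300 ms", followed by "a later time window (300-450 ms) corresponding to lexical-phonological encoding in previous studies". The same section says that the analyses also run on every time frame of the ERP period and include segmentation into micro-states. L1 and L2 patterns are to be compared on amplitude, duration and sequence. The stimulation effect is placed in an early window before vocalization, without saying which of the three. The expected result is stated as follows: "We will expect an interaction between language and stimulation, due to the fact that left DLPFC excitatory rTMS will modulate L2 more than L1".

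Two statements under Aim bear on this. Hypothesis 1 is that excitatory rTMS "will increase performance and/or decrease response time in naming, particularly in L2 naming". Hypothesis 2 adds: "The latency of the ERP modulation by rTMS in L2 will allow us to target the dynamics", together with the planning processes behind better naming.

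The Behavioral analysis section compares naming and translation performance "as well as speech onset latencies in both languages". Nothing links those speech onset latencies to the ERP analysis. No response-locked or latency-adjusted ERP analysis is described.

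**The concern.** The cells compared in hypothesis 2 are the cells in which hypothesis 1 allows naming speed to change. If a process keeps its strength and generators but arrives earlier in L2 under excitatory rTMS, a test at a fixed time after the picture compares different points of the same process. Field power then differs because one waveform is further along. Topography differs because one condition has already moved to the next map.

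A speed-up common to both languages would look like a main effect of stimulation. A larger speed-up in L2 would look like the Language x Stimulation interaction that the plan predicts.

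What is at stake is the stage claim. Hypothesis 2 reads the time of the ERP difference as evidence of which planning process rTMS changed. Without a way to separate timing from strength or configuration, that reading could name the wrong stage. The behavioural tests are not affected.

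**Working it through.** The plan states no ERP effect size, component width or latency difference, so there is no figure to reproduce. The calculation asks only whether a pure shift of modest size could matter for these windows.

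**Inputs from the documents.** Windows: 0-200, 200-300 and 300-450 ms. Lexical selection: 170-270 ms after the picture. Direction under hypothesis 1: faster.

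**Assumptions.** Shifts of 20 and 40 ms earlier. For step 2, also a Gaussian component of constant amplitude, centred at (170 + 270)/2 = 220 ms, with SD 35 or 50 ms.

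**Step 1: where the plan's own interval falls.**
- No shift, 170-270 ms: 30 of 100 ms lie before 200 ms and 70 after (30%/70%). The 200 ms boundary already cuts the stage.
- 20 ms earlier, 150-250 ms: 50%/50%.
- 40 ms earlier, 130-230 ms: 70%/30%.

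**Step 2: window means.** For a unit-area component with centre μ and SD s, the mean over window (a, b) is [Φ((b-μ)/s) - Φ((a-μ)/s)]/(b-a). Values are multiplied by 1000.

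| SD | Centre | 0-200 ms | Change | 200-300 ms | Change |
|---|---|---|---|---|---|
| 35 | 220 | 1.419 | | 7.050 | |
| 35 | 200 | 2.500 | +76% | 4.979 | -29% |
| 35 | 180 | 3.581 | +152% | 2.836 | -60% |
| 50 | 220 | 1.723 | | 6.006 | |
| 50 | 200 | 2.500 | +45% | 4.772 | -21% |
| 50 | 180 | 3.276 | +90% | 3.364 | -44% |

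Worked case, SD 35, first window: Φ((200-220)/35) = Φ(-0.571) = 0.2839, and 0.2839/200 = 1.419 per 1000. At centre 200 ms, Φ(0) = 0.5 and 0.5/200 = 2.500 per 1000. The ratio is 2.500/1.419 = 1.76.

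**Step 3: the interaction.** Suppose L1 does not shift and L2 arrives 20 ms earlier under excitatory rTMS (SD 35). The Language x Stimulation contrast is (2.500 - 1.419) - 0 = +1.081 in the first window and (4.979 - 7.050) - 0 = -2.071 in the second. Both come from timing alone.

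**Step 4: does testing every frame help?** The largest frame-by-frame difference between the shifted and unshifted curves, as a share of peak, is 34% (20 ms) to 62% (40 ms) with SD 35, and 24% to 46% with SD 50. Frame-wise tests on the picture clock therefore show the shift as a difference too. They do not say whether it is timing or strength.

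**Step 5: do the micro-states help?** They could. The same maps in the same order with changed onset or duration would point to timing. However, duration and sequence are stated only for the L1/L2 comparison, and onset is not named as an outcome.

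**The case against.** Several points on the other side stand.

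- **Micro-states are planned.** A reader might infer that any timing shift would inevitably be misread as changed activity. The documents do not support that, because the segmentation can show a shift. What is missing is its use for stimulation and the interaction.
- **The speed change is conditional.** Hypothesis 1 is worded "Excitatory rTMS applied to the left DLPFC will increase performance and/or decrease response time in naming", so faster naming is one option, and it is stated for excitatory rTMS. A reader might also infer slower naming in L2 at baseline, or slowing under inhibitory rTMS. The documents state neither; they say only that L2 lexical access needs more left frontal activation.
- **The change may arise later.** The switching task allows 3500-4500 ms to name the object, and no stage is named for the speed-up. If it arises after 450 ms, the planned windows are untouched. It would be too strong to say that a behavioural latency effect by itself implies the ERP interaction.
- **Earlier arrival is itself a finding.** Hypothesis 2 is about dynamics, so a timing shift would be a substantive result and not merely a repeat of the behavioural one. It still has to be reported as timing.
- **The model is simple.** One isolated component ignores other activity in the first window, such as early visual responses, so the percentages apply to the component and not to the recorded signal.
- **The plan is brief.** It refers to the principles of the group's earlier work, which cannot be seen here and might include such a check.

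None of this supplies a stated means of separating timing from strength.

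**Conclusion.** The point holds as a cheap improvement to the plan. The data remain usable and the planned ERP tests are not invalid, but the step from the time of an ERP effect to a named planning stage is under-supported. Timing alone could produce the predicted interaction if three conditions are met: naming speed changes, it changes more in L2, and the change arises before 450 ms. The documents settle none of the three. The size (+45% to +152% in the first window, -21% to -60% at 200-300 ms) is an illustration that rests on the assumed centre, SD and shifts. It shows that shifts of 20-40 ms are large enough to matter with these windows; it does not predict what the study will find.

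**What to change.** 1. Add response-locked epochs, aligned to each trial's speech onset and ending before articulation, and run the same Language x Stimulation tests on them.
2. Name micro-state onset and duration as outcomes, and test them for the stimulation effect and the interaction as well as for L1 against L2.
3. State that picture-locked effects will be interpreted together with these results, and that an effect will be described as a timing shift when the same map sequence occurs with changed onset or duration.

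Do not require an effect to survive matching of trials on naming latency. Latency is a post-stimulation outcome that rTMS is predicted to change, so matching would select unusual trials and could discard real effects that act through speed.

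The cost is offline work on EEG and speech onset data that the study already plans to collect, with nothing new for participants. The additional tests add to multiplicity and should be declared as supporting analyses. Response-locking blurs activity driven by the stimulus, so it should supplement the picture-locked analysis and not replace it.
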